## 2.0 OBJECTIVES AND SCIENTIFIC AIMS

Primary Objective: To obtain a preliminary efficacy assessment for ribavirin monotherapy among patients with R/M HPV-related malignancies

Secondary Objectives:

- (1) To describe overall survival and progression-free survival;
- (2) To describe the safety and tolerability of ribavirin in this patient population
- (3) To explore Gli-1 expression, as detected by immunohistochemistry (IHC) in pre-treatment archived pathology samples, as a candidate biomarker for efficacy of ribavirin in these cancers;
- (4) Among subjects who initially respond to ribavirin, to explore if subsequent acquired resistance is associated with increased Gli-1 expression.

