## 9.0 TREATMENT/INTERVENTION PLAN

### 9.1 Clinical Plan

Study subjects will self-administer ribavirin 1400 mg PO BID (total dose, 2800 mg/day).

Ribavirin should be taken with food, not in a fasting condition.

All patients will complete pill diaries to document administration of study drug. Patients should be instructed to bring completed pill diaries and all pill bottles to each visit.

Cycle length is 28 days with continuous dosing. Clinic visits for safety assessments and routine laboratory studies will occur weekly in Cycle 1, in weeks 1 and 3 of Cycle 2, and on Week 1 of subsequent cycles ( $\pm$  3 days). Although clinic visits and lab tests should generally occur on the same day each week to facilitate continuity with providers, there is no requirement regarding the day of the week of these visits.

Toxicities will be graded according to NCI CTCAE version 4.

Cross sectional imaging (CT or MRI) is obtained at baseline and q2 cycles. Imaging scans will be scheduled to occur in the last week ( $\pm$  2 days) of each even-numbered cycle. However, after completion of cycle 4, the interval between scans may be increased to q3 cycles, at the discretion of the investigator.

Response assessments will follow RECIST 1.1 criteria (See Section 12).

Patients may remain on study until disease progression or unacceptable toxicity. There will be a post-treatment visit 30 days ( $\pm$  7 days) from last dose of drug for patients who maintain active follow up. If a patient is unable to attend the post-treatment visit due to medical or logistical issues or lost to follow-up, this will not be a protocol violation.

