## 11.1 TOXICITIES/SIDE EFFECTS

### 11.2 General Considerations

#### Ribavirin Toxicities:

Hematologic: anemia, thrombocytopenia, leukopenia, lymphopenia

Gastrointestinal: anorexia, nausea, diarrhea

Hepatic: elevated liver function tests

Pulmonary: dyspnea, cough

Reproductive: may be teratogen

Constitutional: fatigue, musculoskeletal pain

Dermatologic: alopecia, pruritus, rash

Neurologic: headache, dizziness

Endocrine and metabolic: hyperuricemia

The listed ribavirin toxicities include those side effects described in the treatment of hepatitis C in which ribavirin may be given in combination with peginterferon alfa [13-16], and those side effects described in other settings including oncology research in which ribavirin was given at doses up to 1400 mg po BID [37][17, 21].

Even when the patient meets criteria for continued treatment at full dose per the protocol, the investigator retains the discretion to delay the next treatment and/or reduce ribavirin dose if there are safety concerns and/or logistical issues. Any dose reductions not specified in the protocol should be discussed with the principal investigator.

Doses that have been reduced for toxicity must not be re-escalated.

Treatment delays of up to 21 total days per cycle are allowed in a given cycle. Any patient who requires a treatment delay of >21 days, for medical and/or logistical reasons, in a given cycle should be removed from study.

If an investigator feels that a patient requires a dose reduction and/or dose delay other than those specified herein, this may be allowed after communication with the Principal Investigator, and would not be considered protocol violation. If the Principal Investigator is unavailable, Co-PI or designated covering investigator may address such issues as they arise.

Dose modification guidelines in this section are only for those adverse events thought to be at least possibly related to ribavirin.

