### Absolute Neutrophil Count (ANC) and Platelets

ANC (K/mcL) and Platelet Count (K/mcL)
ANC $\geq 1.0$ and Plts $\geq 100$ : Treat without dose reduction.
ANC $< 1.0$ and/or Platelets $< 100$ : Hold. If repeat ANC the next week $\geq 1.0$ and repeat Plts next week $\geq 100$ , resume treatment. Dose reduction by one dose level is not mandatory, but is allowed at the discretion of the investigator.
Febrile Neutropenia *. Hold until resolution. When ANC $\geq 1.5$ and afebrile and Plts $\geq 100$ , may proceed but reduce by 1 dose level

Dose delays and dose reductions are not required for uncomplicated leukopenia, uncomplicated lymphopenia, or other abnormal values in the complete blood cell count (other than hemoglobin ANC, and platelets) without clinical consequence.

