### 14.0 BIOSTATISTICS

A sample size of 12 patients will be accrued and followed until progression of disease (or until removal of study for other medical/logistical reasons), in this pilot study with the objective to obtain preliminary evidence of efficacy in the selected patient population of R/M HPV related malignancies. Radiographic responses, determined by RECIST 1.1 criteria, will be tabulated by adding partial responses and complete responses (CR + PR). The best response for each patient during the study will be used.

Efficacy considerations for the statistical design of this study are informed by historical data regarding second-line or greater systemic therapy for patients with recurrent/metastatic (R/M) head and neck cancer, cervical cancer, or anal cancer. Among patients with R/M head and neck cancer, the historical estimate for objective response rate with palliative chemotherapy after first line is 15% [39, 40]. Similarly, the response rate of palliative single agent chemotherapy for advanced cervical cancer is approximately 15-20% [41, 42]. For R/M anal cancer, no regimen has been shown to be effective after first line platinum + 5-fluorouracil [43].

The regimen would be considered worthy of further study if radiographic responses are observed in at least 2 of 12 subjects. The probability of missing an effect (observing 0 or 1 responses out of 12 patients if the true response rate is 30%), is 0.09. Overall Survival and Progression-Free Survival will be estimated with the Kaplan-Meier method.

Tissue correlative studies will be for purposes of hypothesis generation. We will explore if the anti-Gli-1 IHC score (scale 0-3 dichotomized to low/high) is related to response (CR+PR) using Chi-square or Fisher's exact test. The following provisional scoring system will be used (% refers to percentage of tumor cells that stain positively [cytoplasm and/or nucleus] for Gli 1):

IHC score 0: <=5%

IHC score 1: >5 and <=30%

IHC score 2: >30% and <=50%

IHC score 3: >50%

Additionally, baseline and post-progression Gli-1 expression will be reported (using this provisional scoring system) among the patients who have an initial radiographic response and a post-progression biopsy.

The number and grade of toxicities will be tabulated using NCI CTCAE version 4, as well as the number of dose reductions in all cycles.

The projected accrual rate is 1 to 2 patients per month.

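### Section 14 measures dose modification only by counting reductions, so holds, toxicity discontinuations and the dose actually received go unreported for the tolerability objective

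*Combined protocol and SAP*

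**What the plan says.** Section 2.0 lists as a secondary objective "To describe the safety and tolerability of ribavirin in this patient population". The analysis that serves it is a single sentence in Section 14.0. Its first half covers adverse events: "The number and grade of toxicities will be tabulated using NCI CTCAE version 4". Its second half holds the only item on dosing: "as well as the number of dose reductions in all cycles".

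The planned dose is 2800 mg/day, and Section 9.1 adds: "Cycle length is 28 days with continuous dosing". The Dose Modification Scheme goes down to 2000, 1600 and 1200 mg/day. On interruptions, Section 11.2 says: "Treatment delays of up to 21 total days per cycle are allowed in a given cycle". Beyond 21 days in a cycle the patient is removed (Sections 11.2 and 13.0).

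Some toxicity rules interrupt drug and leave the reduction optional. For neutrophils and platelets the text is: "Dose reduction by one dose level is not mandatory, but is allowed at the discretion of the investigator".

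Section 9.1 also provides an exposure record: "All patients will complete pill diaries to document administration of study drug". No analysis of the diaries is described anywhere.

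**The concern.** Tolerability includes whether patients could stay on the intended dose. The toxicity table shows which events occurred and how severe they were. The only planned figure on what happened to dosing is the reduction count.

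That count responds to one of the ways in which this protocol manages toxicity and not to the others. A patient whose drug is held repeatedly and restarted at the same level adds nothing to it. Nor does a patient who is removed from full dose after a delay of more than 21 days, or for treatment-related Grade 4 diarrhea. Delays for logistical reasons, which Section 11.2 permits, need not appear in either planned tabulation.

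At stake is how well the report answers the second secondary objective. A reader deciding whether this dose can be delivered would not learn how much of it was.

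**Working it through.** **The plan's own figure.** Section 14.0 computes one design quantity, the chance of 0 or 1 responses in 12 at a true rate of 30%. It is 0.7^12 + 12 × 0.3 × 0.7^11 = 0.0138 + 0.0712 = 0.0850, which agrees with the stated 0.09. Nothing below depends on it.

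**Step 1: which rules feed the reduction count.**

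Hold required or permitted, reduction not mandatory:
- ANC below 1.0 or platelets below 100 (ANC and Platelets)
- liver-table holds carrying footnote 1 (11.3.1)
- bilirubin above ULN up to 1.5 × ULN (11.3.2)
- raised creatinine with CrCl of at least 45 ml/min (11.4)
- Grade 1–2 diarrhea, and Grade 3 diarrhea of 48 hours or less (11.5)
- other non-hematologic events of Grade 3 or more that resolve within 7 days (11.7)

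Reduction mandatory, or resumption only at a lower level:
- the hemoglobin triggers and any red-cell transfusion (11.3)
- febrile neutropenia (ANC and Platelets)
- liver-table holds carrying footnote 2 (11.3.1)
- bilirubin above 1.5 × ULN (11.3.2)
- CrCl below 45 ml/min (11.4)
- Grade 3 diarrhea beyond 48 hours (11.5)
- prolonged nausea or vomiting of Grade 3 or more (11.6)
- other events of Grade 3 or more that take longer than 7 days to resolve (11.7)

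The count sees the second list. It need not see the first.

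**Step 2: dose received in one cycle with 0 reductions.** Inputs are 2800 mg/day and 28 days, so 78,400 mg is planned per cycle, and *h* is the days held. The documents do not say whether a hold uses up days of a fixed cycle or lengthens the cycle, so both readings are shown.

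- Fixed cycle: relative dose = (28 − h)/28
- Lengthened cycle: relative dose intensity = 28/(28 + h)

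| Days held | Fixed 28-day cycle | Cycle lengthened |
|---|---|---|
| 7 | 21/28 = 75% | 28/35 = 80% |
| 14 | 14/28 = 50% | 28/42 = 66.7% |
| 21 (maximum) | 7/28 = 25% (19,600 of 78,400 mg) | 28/49 = 57.1% |

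**Step 3: comparison with the reduced levels taken without a break.**

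- Minus 1: 2000/2800 = 71.4%, the same as 28 × (1 − 0.714) = 8 days held in a fixed cycle
- Minus 2: 1600/2800 = 57.1%, or 12 days held
- Minus 3: 1200/2800 = 42.9%, or 16 days held

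In a fixed cycle, more than 8 days held delivers less than level minus 1, and more than 16 days less than level minus 3, each with a count of 0. If cycles lengthen, 21 days held delivers the same intensity as level minus 2, which is two reductions down.

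**Step 4: the two cycles before the first on-treatment scan.** With total days held H, the formulas are (56 − H)/56 and 56/(56 + H).

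- 7 days in each cycle: 42/56 = 75%, or 56/70 = 80%
- one 21-day hold: 35/56 = 62.5%, or 56/77 = 72.7%
- 21 days in each cycle: 14/56 = 25%, or 56/98 = 57.1%

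**The case against.** The strongest reply is that the reduction count does not stand alone. The same sentence tabulates the number and grade of toxicities, so an event that triggers a hold is recorded with its grade. This stands. A reader might infer that the planned summary would present heavily interrupted patients as tolerating ribavirin well. The documents do not support that, because such a patient could show repeated graded events. What stays hidden is the time off drug and the dose lost.

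A reader might also infer that the count would rank a patient held 21 days in every cycle above one who took level minus 3 throughout, although the first received less drug. That holds only for a fixed 28-day cycle (25% against 42.9%). If holds lengthen the cycle, the first patient has 57.1% and the misordering disappears.

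Further points stand in part:

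- The 21-day case is a limit. The Section 11.7 route makes a lower level mandatory once resolution takes more than 7 days, and neutrophils and platelets are rechecked after a week. Reaching the cap in every cycle would need repeated or prolonged holds, with the investigator never choosing to reduce or to remove the patient.
- Anemia, which Section 11.3 names as the leading cause of reduction, is counted.
- Ribavirin's multiple-dose half-life is given as 274–296 hours (about 11 to 12 days), so a short hold lowers drug levels by less than it lowers dose taken.
- Section 9.1 asks patients to bring pill bottles to visits but describes no pill count, so the diary is the only dosing record by the patient that can be assumed.

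None of this supplies the missing information on holds, dose received or discontinuations.

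**Conclusion.** The point holds as a reporting gap. The only planned measure of dose modification can be 0 when delivered dose in a cycle is 25% of plan (fixed cycle) or 57.1% (lengthened cycle), so it can misstate how much drug was tolerated under either reading. One 7-day hold per cycle, a milder case, gives 75–80%. The likely size cannot be judged, because the documents give no expected frequency or length of holds.

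It would be tempting to add that the gap undermines the primary conclusion, since few responses could reflect little drug. The documents do not support that. The rule of at least 2 responses in 12 judges the regimen as given, interruptions included, and its operating characteristics do not change. The diaries would also remain available for a descriptive look at dosing. This is a minor improvement to a secondary, descriptive objective.

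**What to change.** In Section 14.0, keep the toxicity tabulation and replace the reduction-only count with a table, per patient and overall, drawn from the pill diaries and dosing records:

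- number and total days of holds, with reasons (toxicity or logistical)
- number of reductions and lowest dose level reached
- discontinuations for toxicity, including removals after a delay of more than 21 days where toxicity was the cause
- relative dose intensity against 2800 mg/day, before the first response scan and over all cycles

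State whether a hold extends the cycle for this calculation. That is a definition for the analysis and changes no treatment rule. List each patient's best response beside relative dose intensity, descriptively only, since 12 patients cannot support an analysis of that relation.

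The cost is a few lines of text, one table, and the entry and cleaning of diary data for 12 patients. No visits, procedures or patients are added.

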### 15.1 RESEARCH PARTICIPANT REGISTRATION AND RANDOMIZATION PROCEDURES

#### 15.2 Research Participant Registration

Confirm eligibility as defined in the section entitled Criteria for Patient/Subject Eligibility.

## MEMORIAL SLOAN-KETTERING CANCER CENTER

IRB#: 14-211 A (7)

APPROVED: 19 DEC 2016

Obtain informed consent, by following procedures defined in section entitled Informed Consent Procedures.

During the registration process registering individuals will be required to complete a protocol specific Eligibility Checklist.

All participants must be registered through the Protocol Participant Registration (PPR) Office at Memorial Sloan-Kettering Cancer Center. PPR is available Monday through Friday from 8:30am – 5:30pm at [contact]. Registrations must be submitted via the PPR Electronic Registration System (<http://ppr/>). The completed signature page of the written consent/RA or verbal script/RA, a completed Eligibility Checklist and other relevant documents must be uploaded via the PPR Electronic Registration System.

### 15.3 Randomization

Not applicable. There is no randomization in this study.

## 16.1 DATA MANAGEMENT ISSUES

A Research Study Assistant (RSA) will be assigned to the study. The responsibilities of the RSA include project compliance, data collection, abstraction and entry, data reporting, regulatory monitoring, problem resolution and prioritization, and coordinate the activities of the protocol study team. The data collected for this study will be entered into a secure database. Source documentation will be available to support the computerized patient record.

### 16.2 Quality Assurance

Weekly registration reports will be generated to monitor patient accruals and completeness of registration data. Routine data quality reports will be generated to assess missing data and inconsistencies. Accrual rates and extent and accuracy of evaluations and follow-up will be monitored periodically throughout the study period and potential problems will be brought to the attention of the study team for discussion and action.

### 16.3 Data and Safety Monitoring

The Data and Safety Monitoring (DSM) Plans at Memorial Sloan-Kettering Cancer Center were approved by the National Cancer Institute in September 2001. The plans address the new policies set forth by the NCI in the document entitled "Policy of the National Cancer Institute for Data and Safety Monitoring of Clinical Trials" which can be found at:

<http://cancertrials.nci.nih.gov/researchers/dsm/index.html>. The DSM Plans at MSKCC were established and are monitored by the Office of Clinical Research. The MSKCC Data and Safety Monitoring Plans can be found on the MSKCC Intranet at:

[http://mskweb5.mskcc.org/intranet/\\_assets/\\_tables/content/359709/DSMPlans07.pdf](http://mskweb5.mskcc.org/intranet/_assets/_tables/content/359709/DSMPlans07.pdf)

There are several different mechanisms by which clinical trials are monitored for data, safety and quality. There are institutional processes in place for quality assurance (e.g., protocol monitoring, compliance and data verification audits, therapeutic response, and staff education on clinical research QA) and departmental procedures for quality control, plus there are two institutional committees that are responsible for monitoring the activities of our clinical trials programs. The committees: *Data and Safety Monitoring Committee (DSMC)* for

## MEMORIAL SLOAN-KETTERING CANCER CENTER

IRB#: 14-211 A (7)

APPROVED: 19 DEC 2016

Phase I and II clinical trials, and the *Data and Safety Monitoring Board (DSMB)* for Phase III clinical trials, report to the Center's Research Council and Institutional Review Board.

During the protocol development and review process, each protocol is assessed for its level of risk and degree of monitoring required. Every type of protocol (e.g., NIH sponsored, in-house sponsored, industrial sponsored, NCI cooperative group, etc.) will be addressed and the monitoring procedures will be established at the time of protocol activation.

### **17.1 PROTECTION OF HUMAN SUBJECTS**

Potential risks to human subjects include drug related toxicity, pain and discomfort associated with ribavirin side effects (Section 11), phlebotomy, and possible psychological discomfort from the stresses associated with obtaining imaging studies (eg, CT scan), and possible risks associated with research biopsy. All efforts will be made to avoid any complication by completely reviewing patients' symptoms, providing appropriate management, and monitoring blood tests.

If an adverse medical event occurs, the patient will first contact his/her study doctor, a research nurse, or the Principal Investigator. At nights and on weekends, there is an oncology physician on call at all times. Patients may either call or come directly to the Urgent Care Center at Memorial Hospital (or to their local emergency room) to be seen. Patients suffering serious adverse reactions must be carefully followed and all follow-up information also recorded.

Participation in this trial is voluntary. All patients who participate in the study must provide written informed consent.

The patient will be responsible for all costs related to treatment and complications of treatment. Costs to the patient (third party insurer) will include the costs hospitalizations, routine blood tests and diagnostic studies, office visits, baseline EKG, and doctor's fees. Patients will not be charged for ribavirin or any research tests performed on research specimens (research biopsy, immunohistochemistry).

### **17.2 Privacy**

MSKCC's Privacy Office may allow the use and disclosure of protected health information pursuant to a completed and signed Research Authorization form. The use and disclosure of protected health information will be limited to the individuals described in the Research Authorization form. A Research Authorization form must be completed by the Principal Investigator and approved by the IRB and Privacy Board (IRB/PB).

### **17.3 Serious Adverse Event (SAE) Reporting**

An adverse event is considered serious if it results in ANY of the following outcomes:

- Death
- A life-threatening adverse event
- An adverse event that results in inpatient hospitalization or prolongation of existing hospitalization

## MEMORIAL SLOAN-KETTERING CANCER CENTER

IRB#: 14-211 A (7)

APPROVED: 19 DEC 2016

- A persistent or significant incapacity or substantial disruption of the ability to conduct normal life functions
- A congenital anomaly/birth defect
- Important Medical Events (IME) that may not result in death, be life threatening, or require hospitalization may be considered serious when, based upon medical judgment, they may jeopardize the patient or subject and may require medical or surgical intervention to prevent one of the outcomes listed in this definition

**Note:** Hospital admission for a planned procedure/disease treatment is not considered an SAE.

SAE reporting is required as soon as the participant signs consent. SAE reporting is required for 30-days after the participant's last investigational treatment or intervention. Any events that occur after the 30-day period and that are at least possibly related to protocol treatment must be reported.

If an SAE requires submission to the IRB office per IRB SOP RR-408 'Reporting of Serious Adverse Events', the SAE report must be sent to the IRB within 5 calendar days of the event. The IRB requires a Clinical Research Database (CRDB) SAE report be submitted electronically to the SAE Office as follows:

Reports that include a Grade 5 SAE should be sent to [[contact]](mailto:[contact]). All other reports should be sent to [[contact]](mailto:[contact]).

The report should contain the following information:

Fields populated from CRDB:

- Subject's initials
- Medical record number
- Disease/histology (if applicable)
- Protocol number and title

Data needing to be entered:

- The date the adverse event occurred
- The adverse event
- The grade of the event
- Relationship of the adverse event to the treatment (drug, device, or intervention)
- If the AE was expected
- The severity of the AE
- The intervention
- Detailed text that includes the following
  - A explanation of how the AE was handled
  - A description of the subject's condition
  - Indication if the subject remains on the study
- If an amendment will need to be made to the protocol and/or consent form
- If the SAE is an Unanticipated Problem

